Specific Aim 2: Determine the safety of insulin glargine 0.4 unit/kg early administration within four hours from IV Insulin infusion initiation.

III. METHODS

A. Study Design and Methodology:

This will be a prospective, open-label, intervention cohort study including all consecutive adult patients with Diabetes Ketoacidosis (DKA) getting admitted to Fairview Hospital-Medical Intensive Care Unit (FV-MICU). Screening of patient eligibility and informed consent will be done by the MICU admitting physician once the patient gets admitted to MICU. Participants will be given an overview of the study, including study procedures, and potential risks. Participants will be given adequate time to review the consent form and have opportunities to ask questions. After the informed consent process has been completed and a consent form has been signed, a copy of the consent will be provided to the participant and another copy will be secured in the Principle Investigator office in a locked cabinet. Enrolled participants in the intervention group will receive an Insulin Glargine 0.4 Unit/kg within 4 hours from initiating the IV Insulin Infusion, as per the Cleveland Clinic DKA protocol. The remaining of the management will be following the CC DKA protocol including continuing IVII till Anion Gap Closure ($AG \leq 12$), Basal Metabolic Panel Q 2 hrs, and replacing electrolytes as indicated. After closing the anion gap, the decision for giving more Basal Insulin doses will be left to the treating physician's discretion. For patient safety, Point Of Care (POC) blood glucose will be checked hourly before IVII discontinuation. After IVII discontinuation, the BG will be checked with meals, bedtime and 2 am if the patient maintain good oral intake, if not, the BG will be checked q 4 hrs. Target BG 150 – 200 mg/dl during the DKA management and 140 – 180 mg/dl after DKA resolution as per American Diabetes Association recommendations. In case of any hypoglycemia event, this goal will be achieved by using Dextrose containing fluid or carbohydrate enriched oral intake which will be left to the treating physician discretion depending on patient awareness and severity of hypoglycemia. Also, the pre meals and correctional insulin doses after AG closure will be left to the treating physician's discretion. After AG closure the pre meals and correctional insulin doses will be left to the treating physician's discretion. In case of not closing the AG after 24 hours from the initial Glargine dose, the decision for further Glargine doses will be left to the treating physician's discretion.

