
The investigator team will be notified by the MICU attending after each participant enrollment, so one of the team members will present to MICU to collect the data prospectively in a standardized Data Collecting Sheet (DCS) by using REDCap and all protected health information (PHI) will be de-identified. As regards the control group, an E-research request will be submitted to provide a list by

all the consecutive adult patients admitted to FV-MICU with a diagnosis of DKA in the period between January 1st 2019 till the date of IRB approval. Prespecified sample size and matched in basal patient characteristics and DKA severity will be selected as the control group. Data will be collected retrospectively for the control group and will be recorded directly into the DCS in RedCap. Clinical outcomes will be compared between the intervention and control groups. The primary outcome includes time to anion gap closure ($AG \leq 12$). Secondary outcomes include hospital Length Of Stay (LOS), ICU LOS, total IVII dose, the incidence of transitional failure (defined recurrence of DKA after initial IVII discontinuation within 24 hours and requiring reinitiating the IVII), the incidence of hyperglycemia (> 180 mg/dL) and hypoglycemia (defined as ≤ 70 mg/dL, <54 , <40) during 24 hours from Insulin Glargine administration.

B. Definition of main exposures and outcomes:

Diagnosis of DKA will be made by ICD-10-CM code E10.10, E11.10, or meeting the ADA definition; $BG \geq 250$ mg/dl, $AG > 12$, and positive Ketones in serum or urine

DKA classification as the following table from ADA:

	Mild (plasma glucose >250 mg/dl)	Moderate (plasma glucose >250 mg/dl)	Severe (plasma glucose >250 mg/dl)
Arterial pH	7.25–7.30	7.00 to <7.24	<7.00
Serum bicarbonate (mEq/l)	15–18	10 to <15	<10

For the hyperglycemia analysis, patients will be compared in the following categories according to their mean or median (depending on the normality of the data distribution) blood glucose throughout the hospital stay:

- Mean/median BG <80 mg/dL
- Mean/median BG 81-100 mg/dL
- Mean/median BG 101-140 mg/dL
- Mean/median BG 141-180 mg/dL
- Mean/median BG > 180 mg/dL'
- Mean/median BG > 240 mg/dL

Hypoglycemia will be defined by three categories:

- any glucose level below 70 mg/dL
- any glucose level less than 54 mg/dL
- any glucose level less than 40 mg/dL

For Time of Anion Gap Closure (TAGC) will use the ADA definition: $AG \leq 12$ mEq/L

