Transitional failure will be defined as the recurrence of DKA ($BG \geq 250$ mg/dl, $AG > 12$, and positive Ketones in serum or urine) after initial IVII discontinuation within 24 hours and requiring reinitiating the IVII.

C. Study Population

Intervention vs Control group

- Intervention group: All consecutive adult patients getting admitted to FV- MICU and meet the inclusion criteria and accepted to receive insulin glargine early as per the protocol. They will receive insulin glargine 0.4 unit/kg within 4 hours from initiating the IV Insulin Infusion, as per the Cleveland Clinic DKA protocol.
- Control group: prespecified and matched sample size, consecutive adults who admitted to FV-MICU with a diagnosis of DKA in the period between January 1st 2019 till the IRB approval date and didn't receive basal insulin before AG closure.

Inclusion criteria:

- Age \geq 18 years old
- Meet DKA definition as above
- Having the capacity to sign Informed consent

Exclusion Criteria

- IV insulin infusion initiated more than 4 hours.
- Persistent hypotension (SBP<80 mmHg despite receiving 1000cc normal saline).
- Require Vasopressor
- Acute Coronary Syndrome
- Pregnant
- End-stage renal disease
- Unwilling to consent to participate in the trial
- Currently under police custody
- Transferred from another hospital
- Require emergent surgery
- Alcoholic Ketoacidosis

Study Variables:

General Informations:

- Patient name
- MRN
- Age
- Sex (Male, Female, Others)
- Race (White, Black, Asian, Other)
- Ethnicity (Hispanic vs. Non-Hispanic)
- Weight on admission (kg)
- BMI (Kg/m²)
- Height (cm)
- Date of Hospital admission
- Date of ICU admission

- Date of DKA diagnosis (MM/DD/YY)
- Precipitating cause of DKA
 - Noncompliance
 - New-onset
 - Infection
 - Cerebrovascular accident
 - alcohol abuse
 - pancreatitis
 - Drugs
 - Others

Past Medical history

- Type of diabetes:
 - Type 1 DM
 - Type 2 DM
 - Cystic fibrosis-related diabetes
 - Steroid-induced diabetes
 - Other or no clear diagnosis
- Known diagnosis of other major medical comorbidities (CAD, CHF, HTN, COPD, asthma, liver disease, CKD, cancer, other)
- On Renal Replacement Therapy (Y/N)
- Using Basal insulin at home (Yes/No/ unknown)
- If previous point answer is yes check the corresponding insulin type and write the dose: (Glargine, Detemir, Degludec, NPH, Continuous Insulin Pump) (dose: IU)
- Home total basal insulin dose (units)

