- Non-insulin antihyperglycemics taken at home prior to admission, including the type
 - Sulfonylureas
 - Thiazolidinediones
 - Dipeptidyl peptidase-4 (DPP-4) inhibitors
 - Biguanides
 - Glucagon like peptide-1 (GLP-1) analogues
 - Sodium-glucose transport protein 2 (SGLT2) inhibitors
 - Meglitinides
 - Alpha glucosidase inhibitors
 - Amylin analogues
- History of immunosuppression (history of cancer, HIV or auto-immune disease or organ transplant, chronic steroid)

Initial Laboratory values:

- Anion gap (mEq/L)
- Bicarbonate (mEq/L)
- Glucose (mg/dL)
- Beta-Hydroxybutyrate (mmol/L)
- Ketones in the urine (Y/N/Unknown)
- HbA1c %
- Lactate (mmol/L)

Intervention and outcomes:

- IV insulin infusion starting time
- Insulin glargine administration time
- Anion Gap closure time
- IV insulin discontinuation time
- Number of hours of IVII
- Total IV insulin infusion has been given
- Total IV insulin/weight
- Total IV fluid during DKA management
- Date of discharge from ICU
- Date of discharge from hospital
- Hospital Length Of Stay (days)
- ICU LOS (hours)
- Transitional failure (recurrence of DKA)?

Hypoglycemia Events

- Hypoglycemia event within 24 hrs from glargine
- Time of the hypoglycemia
- How many hours after the glargine administration?
- Severity
- How it has been treated

Hyperglycemia Events

- Hyperglycemia Event after IVII discontinuation by 24 hours (Y/N)
- time of the hyperglycemia event
- Severity of hyperglycemia
- How many hours after IVII discontinuation

D. Outcomes

Primary outcome: Time to anion gap closure (hours).

Secondary outcomes:

- Hospital Length of stay (days)
- ICU length of stay (hours)
- Total IV insulin infusion dose (International unit)
- Incidence of transitional failure (percentage).
- Incidence of hyperglycemia (> 180 mg/dL) during 24 hours from Insulin Glargine administration (percentage).
- Incidence of hypoglycemia (defined as ≤ 70 mg/dL, <54, <40) during 24 hours from Insulin Glargine administration (percentage).

IV. DATA COLLECTION

For the control group, the data will be collected retrospectively and recorded in standardized DCS in RedCap. For the intervention group, the data will be collected prospectively by the investigator team members and observations will be recorded in standardized DCS in RedCap. All protected health information (PHI) will be de-identified for both intervention and control group by using de-identification function in REDCap.

V. DATA ANALYSIS

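### The laboratory entry definition requires no acidosis, so some eligible patients fit no category of the severity table used for matching and may reach the primary endpoint at the first panel

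*Combined protocol and SAP*

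**What the plan says.** Section III.B gives two routes to a DKA diagnosis: "Diagnosis of DKA will be made by ICD-10-CM code E10.10, E11.10, or meeting the ADA definition". The laboratory route is spelled out as "meeting the ADA definition; $BG \geq 250$ mg/dl, $AG > 12$, and positive Ketones in serum or urine". The inclusion criteria in III.C only point back to it ("Meet DKA definition as above"). Neither the inclusion nor the exclusion list sets a pH limit, a bicarbonate limit or a minimum AG above 12.

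pH and bicarbonate thresholds appear only in the table introduced by "DKA classification as the following table from ADA". Its mildest column is pH 7.25–7.30 and bicarbonate 15–18 mEq/l. Section III.A says the controls will be matched on baseline characteristics and DKA severity.

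For the primary endpoint, III.B states: "For Time of Anion Gap Closure (TAGC) will use the ADA definition: $AG \leq 12$ mEq/L". Under III.A the gap is measured on a "Basal Metabolic Panel Q 2 hrs" schedule, and glargine is given "within 4 hours from initiating the IV Insulin Infusion, as per the Cleveland Clinic DKA protocol".

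The study variables in III.C include initial AG, bicarbonate and glucose, but not pH. Section V plans unadjusted comparisons: t-test or Mann-Whitney, one-sided at 0.025.

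**The concern.** The entry definition and the severity table do not cover the same patients. Anyone who meets the three laboratory conditions with bicarbonate above 18 and pH above 7.30 may enter, yet has no severity category. The planned matching on severity has no rule for that patient.

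These are also the patients most likely to start near the endpoint. A patient entering at AG 13 needs a fall of 1 mEq/L, which the first scheduled panel could record before glargine has been given.

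Two things are at stake. If such patients are equally common in both groups, they add observations with little room for a treatment effect and widen the spread, so power falls. If their share differs, the difference enters the primary comparison directly, because the analysis does not adjust for baseline AG.

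Unequal shares are plausible because the groups are filtered differently. Intervention patients are screened at MICU admission, must consent and must be dosed within 4 hours. Controls are taken from records and must not have received basal insulin before AG closure, a condition that rapid closers easily meet. The imbalance could favour either group.

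**Working it through.** **Reading the definitions together.** Take a hypothetical patient with glucose above 250, AG 13, bicarbonate 22, normal pH and positive urine ketones.

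| Step | Rule | Result |
|---|---|---|
| Entry (III.B, III.C) | glucose ≥250, AG >12, ketones positive | eligible |
| Severity (III.B table) | mildest: pH 7.25–7.30, bicarbonate 15–18 | no category |
| Endpoint (III.B) | AG ≤12 | needs a fall of 1 mEq/L |
| First panels (III.A) | every 2 h; glargine up to 4 h after infusion start | one or two panels can precede glargine |

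**The plan's own sample size.** Inputs from Section V: mean 15.6 h, SD 6 h, 20% difference, one-sided α 0.025, β 0.10. Equal allocation is assumed, because no ratio is stated.

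- Δ = 0.20 × 15.6 = 3.12 h.
- n per group = 2 × 36 × (1.960 + 1.282)² / 3.12² = 77.7, so 78 per group and 156 in total (158 with the t distribution). The stated 160 reproduces.
- With 80 per group, SE = 6 × √(2/80) = 0.949 h and power = Φ(3.12/0.949 − 1.96) = 90.8%.

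**How common might early closure be?** The documents give no share. Under a normal reading of 15.6 h, SD 6 h:

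- by 2 h: Φ((2 − 15.6)/6) = 1.2%
- by 3 h: Φ((3 − 15.6)/6) = 1.8%
- by 4 h: Φ((4 − 15.6)/6) = 2.7%

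The case definition behind that baseline is not stated. Its interval of ±2.5 h implies only about (1.96 × 6/2.5)² ≈ 22 patients. A true share of 5% would leave no such patient among 22 with probability 0.95²² = 32%, so the baseline does not exclude 5%.

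**Illustration.** Assumptions not in the documents: a share f closes at 3 h whatever the treatment. The rest follow the planning mean m (15.6 h control, 12.48 h with the planned effect) and SD 6 h. There are 80 per group. The variance must include the mixture:

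- mean = (1 − f)m + 3f
- variance = (1 − f) × 36 + f(1 − f)(m − 3)²

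*Equal share f = 10%.* Means are 14.34 and 11.53 h, a difference of 2.81 h. Variances are 32.4 + 0.09 × 12.6² = 46.69 and 32.4 + 0.09 × 9.48² = 40.49. SE = √((46.69 + 40.49)/80) = 1.044 h. Power = Φ(2.81/1.044 − 1.96) = 77%. Holding SD at 6 h would give 84%, but that contradicts the mixture.

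*Excess in the intervention group only, no glargine effect.* At 10 points the shift is 0.10 × 12.6 = 1.26 h, SE = √((36 + 46.69)/80) = 1.017 h, and the false-positive rate is Φ(1.26/1.017 − 1.96) = 23.6%. At 5 points the shift is 0.63 h, the variance is 34.2 + 0.0475 × 12.6² = 41.74, SE = 0.986 h, and the rate is 9.3%.

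The same formulas at 2%, close to the normal reading above, complete the range:

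| Share or excess | Power, equal share in both groups | False-positive rate, excess in intervention group |
|---|---|---|
| 0 | 91% | 2.5% |
| 2% | 88% | 4.5% |
| 5% | 84% | 9.3% |
| 10% | 77% | 23.6% |

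Simulating the same mixture with the Mann-Whitney test, which Section V specifies for non-normal data, gives about 74–75% power at an equal 10% share. It gives false-positive rates of about 7–8% at a 5-point excess and 18–19% at 10 points.

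**The case against.** The strongest objection is that few such patients will exist. They must be admitted to the MICU, be diagnosed with DKA and be on an insulin infusion, and the unit's own figures suggest 1–3% early closure. A 5–10 point excess in one group is several times that whole share. This stands: the larger figures are illustrations, not expectations. It is limited by the small baseline sample and its unstated case definition.

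A second objection is that severity matching would limit any imbalance. That holds for patients the table can classify. It does not hold for those with no category, and the plan does not say how they would be handled.

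Third, a reader might infer that the definition and the table contradict each other. The documents do not support that. The table is introduced as a classification, so it can be read as grading applied after diagnosis. Nor can the table be assumed to be part of entry: III.B repeats the three-part definition, again without acidosis, for recurrence of DKA. The supportable point is that the two must be reconciled.

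Fourth, it is tempting to say that these patients cannot show a glargine effect. That is too strong. Glargine may be given at any point in the first 4 hours and time zero for the primary outcome is not defined, so some could be dosed before their first panel.

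**Conclusion.** The point holds as a mismatch of definitions. On the text, a non-acidotic patient is eligible, has no place in the severity matching, and may meet the primary endpoint on the first panel, possibly before glargine. Dilution follows if such patients are enrolled. Bias follows only if their share differs between groups, and its direction cannot be predicted.

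The size is unknown because the share is unknown. At about 2% the effect is small: 88% power if equal, or a 4.5% false-positive rate if all are in the intervention group. It becomes material at 5–10%. These figures assume closure at 3 h, 80 per group and the planning mean and SD for everyone else. An excess among controls would work against glargine instead.

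A reader might also infer that the sample size is wrong or that the trial is likely to give a false-positive result. Neither follows: 160 reproduces, and nothing in the documents establishes an imbalance. This is an inexpensive improvement to the definitions, not a defect that invalidates the design.

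**What to change.** In III.B, reconcile the entry definition with the document's own severity table, so that every patient in both groups falls into one of its categories on the initial bicarbonate. State that the same rule applies to the prospective and the historical patients. Initial bicarbonate is already a listed variable. pH is not, so it should not serve as an alternative route; its availability could differ between the groups.

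The cost is a short change to the definition, made before outcomes are known. A few mild admissions become ineligible. Applied to everyone, the rule also means that a diagnosis code alone no longer suffices, so some historical patients without the needed value may be lost.

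The change does not separate entry from endpoint. A patient with AG 13 and bicarbonate 17 would still qualify and could still close on the first panel. The plan should acknowledge this remaining adjacency of AG >12 and AG ≤12.

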The sample size calculation considered the average time of AG closure in the last 3 months in FV-MICU was 15.6 ± 2.5 hours (CI 95%) and SD of 6 hours. Using one-sided α of 0.025 and an β of 0.10, an expected 20% difference between the two groups, a sample size of 160 totally of the participant will be adequate.

Categorical variables will be described as frequency rates and percentages, and continuous variables will be described using mean, median, and interquartile range (IQR). Proportions for categorical variables will be compared by Chi-squared test of Fisher's exact test. Means for continuous variables will be compared by Student's t-test if normally distributed and Mann-Whitney test if not normally distributed. All statistical analyses will be performed with a one-sided p-value < 0.025 to determine statistical significance. All statistical analyses will be completed by study investigators using Statistical Analysis Software (SAS).

VI. DATA AND SAFETY MONITORING PLAN (if applicable)

All data will be stored in a secured REDcap database. No PHI will be saved on non-HIPAA protected devices. All protected health information (PHI) will be de-identified by using RedCap.

To ensure patient safety, CCF Hypoglycemia protocol is getting followed in all patients receiving insulin including our enrolled participants. Before IV insulin discontinuation, the blood glucose level is getting checked hourly as per protocol. Once the AG is closed and insulin infusion is discontinued, the patient who is maintaining oral intake, blood glucose will be checked with meals, bedtime, and 2 am. If the patient having poor oral intake, blood glucose will be checked q 4 hours. Different treatment options for any hypoglycemic events are available in the protocol depending on the severity of the hypoglycemia event and patient awareness, ranging from oral carbohydrate supplement to IV fluid containing dextrose.

VII. STUDY LIMITATIONS

- Retrospective EPIC data review for the control group. Single-center.

VIII. ETHICAL CONSIDERATIONS

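### Whole-stay mean or median glucose is not time-weighted, so hourly checks on the insulin infusion give the DKA phase about three times the weight its duration warrants

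*Combined protocol and SAP*

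**What the plan says.** Section III.B of the combined protocol and SAP sets up a hyperglycemia analysis in which patients are placed in glucose bands, with cuts that include 180 and 240 mg/dL, "according to their mean or median (depending on the normality of the data distribution) blood glucose throughout the hospital stay". It gives no computing rule beyond this: no weighting by time, no restriction to a phase of the stay, and no statement of whether point-of-care values, laboratory values or both enter the summary.

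Section III.A fixes how often glucose is measured. While the infusion runs, "Point Of Care (POC) blood glucose will be checked hourly before IVII discontinuation". Later, "After IVII discontinuation, the BG will be checked with meals, bedtime and 2 am if the patient maintain good oral intake". Patients who are not eating well are measured every four hours instead. Sections VI and VIII repeat this schedule. Section III.A also calls for "Basal Metabolic Panel Q 2 hrs" during DKA treatment, and for "continuing IVII till Anion Gap Closure", which ties infusion time to the primary outcome, time to anion gap closure.

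The bands do not appear in section III.D. The hyperglycemia outcome listed there is the incidence of values above 180 mg/dL in the 24 hours from glargine.

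**The concern.** An ordinary mean or median of glucose values gives each reading equal weight. When sampling is dense in one phase and sparse in the next, the summary describes the dense phase more than its length justifies. Here the dense phase is DKA treatment, when glucose can be expected to be highest, so the unweighted summary is pulled upward.

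Two things are at stake. First, a patient whose time-averaged glucose lies at or below 180 mg/dL may be placed above it. Second, the weight on the DKA phase depends on how long the infusion ran, and the intervention is meant to shorten that. Part of any difference in the bands could then reflect sampling density rather than glucose.

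**Working it through.** **Inputs from the document**
- Control time to gap closure: "FV-MICU was 15.6 ± 2.5 hours (CI 95%) and SD of 6 hours" (section V). A 20% reduction gives 0.8 × 15.6 = 12.48 h for the intervention group.
- Readings on IVII: 1 per hour. Afterwards: 5 a day (three meals, bedtime, 2 am; three meals assumed) or 6 a day (every 4 h).
- Hospital stay: 5.9 d control and 5.1 d intervention. These come from a trial cited in the background and are the only stay figures in the document.

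**Assumptions**
- IVII hours equal hours to gap closure.
- Controls were sampled on the same schedule.
- Mean glucose in each phase is assumed, because the document gives none; a range is shown.

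**The plan's own figure.** The document has no calculation for this analysis. Its one design calculation reproduces: n per group = 2 × (1.960 + 1.282)² × 6² / 3.12² ≈ 78, so 156 in total against the stated 160. It is not in dispute.

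**Weight per hour.** 24/5 = 4.8, or 24/6 = 4.0.

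**Share of readings taken on IVII.** With h hours of IVII, a stay of L days and m readings a day afterwards:

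share = h / [h + (24L − h) × m/24]; time share = h / (24L)

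- Control, m = 5: 15.6 / (15.6 + 26.25) = 37.3%.
- Control, m = 6: 15.6 / (15.6 + 31.5) = 33.1%.
- Time share: 15.6 / 141.6 = 11.0%. The over-representation is 3.4-fold (m = 5) or 3.0-fold (m = 6).
- Intervention (12.48 h, 5.1 d): 35% or 31% of readings.
- Counting a laboratory glucose every 2 h raises the control share to 47% or 43%.

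**When IVII readings become the majority.** The share passes 50% when L < h/24 + h/m. For 15.6 h that is 0.65 + 3.12 = 3.8 d (m = 5) or 0.65 + 2.60 = 3.3 d (m = 6). For 12.48 h it is 3.0 d or 2.6 d. With laboratory glucose counted, the limit for 15.6 h is 5.3 d or 4.6 d.

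**Effect on one patient's band** (15.6 h, 5.9 d, m = 5; patient mean = later mean + difference × share)

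| Assumed mean on / after IVII (mg/dL) | By readings | By time | Crosses 180? |
|---|---|---|---|
| 200 / 160 | 175 | 164 | No |
| 225 / 160 | 184 | 167 | Yes |
| 250 / 170 | 200 | 179 | Yes |

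At 225/160 with m = 6, the reading mean is 160 + 65 × 0.331 = 181.5, still above 180.

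**Dependence on IVII duration.** At 225/160 and 5.9 d, IVII of 9.6, 15.6 and 21.6 h (mean ± 1 SD) gives reading means of 177, 184 and 190 mg/dL with identical glucose in each phase. Time-weighted, they are 164, 167 and 170.

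**The median.** If every IVII reading exceeded every later one, the overall median would sit at 0.5/(1 − 0.373), the 80th percentile of later readings. Weighted by time it would sit at 0.5/(1 − 0.110), the 56th. Choosing the median does not remove the problem.

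**Between-group gap (control minus intervention, mg/dL) with the same glucose per phase**

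| Case | By readings | By time | Excess |
|---|---|---|---|
| 250/170, stay 5.5 d in both (assumed) | 4.6 | 1.9 | 2.7 |
| 225/160, stay 5.9 d in both | 3.6 | 1.4 | 2.2 |
| 250/170, stay 5.9 vs 5.1 d | 1.6 | 0.7 | 0.9 |
| 225/160, stay 5.9 vs 5.1 d | 1.3 | 0.5 | 0.8 |

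The excess is proportional to the assumed difference between phases. At 300/160 with equal stays of 5.9 d it would be 7.8 − 3.1 = 4.7.

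**The case against.** The strongest reply is that the effect is modest and falls on a secondary display. Most of this stands.

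- A reader might infer that the summary mostly reflects the DKA phase. The document does not support that. At its own closure time and the only stay it quotes, roughly a third of point-of-care readings come from IVII, and under half even with laboratory glucose. A majority on point-of-care checks alone needs a stay below about 3 to 4 days, and no local length of stay is given.
- A reader might infer that faster gap closure alone would pass for better glycemic control. The excess due to sampling is about 1–3 mg/dL in the cases worked. Part of the raw gap also survives time weighting, because fewer hours at high glucose is a real difference in exposure.
- A reader might infer that patients are generally misplaced at 180. That depends on the assumed phase means. The glucose targets in section III.A are 150–200 mg/dL during DKA management and 140–180 mg/dL afterwards. At 200/160, the upper end of the first and the middle of the second, both summaries fall in the same band.
- Section III.B does not say in terms that every reading counts equally. It is the natural reading, and nothing else is specified.

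What the reply does not remove is the mismatch between sampling rates, its link to infusion time, or the sensitivity of individual classification near 180.

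**Conclusion.** The point holds in a limited form. Followed as written, the whole-stay mean or median over-weights the IVII phase about three-fold relative to its duration, and that weight moves with a quantity tied to the primary outcome. The main consequence is for individual classification near 180 mg/dL: 184 against 167 at 225/160, but no switch at 200/160. The between-group consequence is small, about 1–3 mg/dL beyond time weighting at the assumed differences of 65 to 80 mg/dL between phases, and larger only if the phases differ much more.

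These sizes rest on assumed phase means, a length of stay borrowed from a cited trial, and equal sampling in both groups. The supporting band comparison in section III.B is affected. The primary outcome, the sample size and the outcomes listed in section III.D are not.

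**What to change.** In section III.B, replace the mean or median of readings with a time-weighted mean glucose per patient: the area under the time-stamped readings divided by the hours elapsed. Use this value for the whole-stay bands. Report it also separately for the periods on and after IVII, so that a difference in infusion time is not read as a difference in glycemic control. Basing the bands on the post-IVII period alone is not needed; that would change the quantity being compared.

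State which readings count (point-of-care, laboratory or both), and apply the same rule to both groups.

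Export the time-stamped glucose series for both groups. The study variables list only the initial glucose and event fields, so a whole-stay summary of any kind needs this export.

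The cost is a few lines of text, a data export and a short calculation. No new measurement and no change to care is involved.

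### Hyperglycemia has three conflicting definitions, the listed 24-hour window starts at different points in the two groups, and the glucose categories overlap

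*Combined protocol and SAP*

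**What the plan says.** Hyperglycemia appears in three places, with three time windows and two kinds of measure.

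- **III.B, Definition of main exposures and outcomes.** The hyperglycemia analysis compares patients by their mean or median "blood glucose throughout the hospital stay". The categories are "Mean/median BG <80 mg/dL", "Mean/median BG 81-100 mg/dL", "Mean/median BG 101-140 mg/dL", "Mean/median BG 141-180 mg/dL", then above 180, and finally "Mean/median BG > 240 mg/dL".
- **III.D, Outcomes (and III.A in the same sense).** The secondary outcome is "Incidence of hyperglycemia (> 180 mg/dL) during 24 hours from Insulin Glargine administration (percentage").
- **III.C, Study Variables, Hyperglycemia Events.** The field collected is "Hyperglycemia Event after IVII discontinuation by 24 hours (Y/N"), with the time, severity and hours since the infusion stopped.

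Section III.C requires that controls had no basal insulin before anion gap closure, whereas the intervention group receives glargine within 4 hours of starting IVII. Section V gives one general sentence: categorical variables are compared by a chi-squared or Fisher's exact test. It does not say which definition of hyperglycemia is tested.

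**The concern.** Three definitions of one outcome allow three different results, and nothing in the plan says which is the result. With an open-label intervention group and retrospective controls, that choice should not be left until the data are seen.

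The listed definition has a further problem. Its clock starts early in treatment for one group and after closure for the other, so the comparison partly measures when observation began.

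The categories in III.B are also not a partition. The band above 180 has no upper limit, so it contains the band above 240, and some values belong to no band. Used as one table, they would place some patients twice and others nowhere.

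**Working it through.** **The plan's own figure (context only).** The one computed design figure is the total of 160 for the primary outcome. With a difference of 0.20 × 15.6 = 3.12 h, SD 6 h, one-sided α 0.025 and power 0.90, n per group = 2 × (1.960 + 1.282)² × 6² / 3.12² ≈ 77.7. That rounds up to 78 per group, 156 in total (about 158 with the t distribution). The stated 160 is reproduced within 3%. Nothing below depends on it.

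**Step 1: the windows side by side.**

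| Place | Measure | Window |
|---|---|---|
| III.B | Mean or median, in categories | Whole hospital stay |
| III.A, III.D | Any value above 180 mg/dL | 24 h from glargine |
| III.C data field | Event, yes/no | 24 h after IVII stops |

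**Step 2: one glucose course under each definition.** This series is invented for illustration. Ten hourly readings fall evenly from 400 to 190, six are at 170 and 25 are at 150. Suppose IVII stops after the sixteenth reading.

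- Mean = (10 × 295 + 6 × 170 + 25 × 150) / 41 = 7,720 / 41 = 188.3, which is in the band above 180.
- Median = 150, which is in the 141-180 band. The mean/median choice alone changes the category.
- 24 h after IVII stops: no value above 180, so no event.
- 24 h from glargine, given within 4 h of starting IVII: values above 180 remain, so an event.
- 24 h from glargine, given after closure at about the sixteenth reading: no event.

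The last two lines are the same glucose course. It counts as an event in the intervention group and as a non-event in a control.

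**Step 3: how far this shift can go.** Patients who enter on the ADA definition start at 250 mg/dL or more (III.B). The target range on infusion is 150 to 200 (III.A), so a patient can be on target and above 180. Section VIII describes a fall of 50 to 100 mg/dL per hour, faster than the series above ((400 − 190) / 9 = 23 per hour). From 400, reaching 180 takes 220 / 50 = 4.4 h or 220 / 100 = 2.2 h. Whether an early window catches the initial high values therefore depends on starting glucose, rate of fall and time of glargine. The documents do not give their distribution, so the shift cannot be sized.

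**Step 4: the categories read literally.**

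| Value (mg/dL) | Categories met |
|---|---|
| 80; 80.5; 100.5; 140.5 | None |
| 180 | 141-180 |
| 180.5; 240 | >180 |
| 240.5; 250 | >180 and >240 |

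**Step 5: size of overlap and gaps.** Assumption, not in the documents: patient mean glucose is normal with mean μ and SD σ. Counted twice = 1 − Φ((240 − μ)/σ). Unassigned = probability of lying in 80-81, 100-101 or 140-141.

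| μ | σ | Counted twice | Of 160 | Unassigned |
|---|---|---|---|---|
| 160 | 30 | 0.4% | 0.6 | 1.3% |
| 160 | 50 | 5.5% | 8.8 | 1.4% |
| 180 | 30 | 2.3% | 3.6 | 0.6% |
| 180 | 50 | 11.5% | 18.4 | 0.9% |
| 200 | 30 | 9.1% | 14.6 | 0.2% |
| 200 | 50 | 21.2% | 33.9 | 0.6% |
| 220 | 30 | 25.2% | 40.4 | 0.04% |
| 220 | 50 | 34.5% | 55.1 | 0.3% |

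The category shares sum to between 99% and 134%.

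**The case against.** Four arguments can be made for the plan.

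1. **The thresholds may be cumulative.** The hypoglycemia list that follows in III.B (below 70, 54 and 40) is nested and is also called categories. If above 180 and above 240 are separate proportions, each compared between groups, nobody is double-counted. A reader might infer that the planned test is invalid. The documents do not support that, because Section V never specifies a six-cell table. What stands is that four of the six items are separate bands, the text does not say that the last two are cumulative, and the list cannot be one table as written.
2. **The listed incidence can still be tested.** A reader might infer that the 24-hour outcome goes unanalysed. The general test in Section V could be applied to it. What stands is that the analysis labelled as the hyperglycemia analysis, and the event field, both use other windows.
3. **Controls may have a glargine time.** Specific Aim 1 contrasts early with late administration, and Section VIII calls dosing after closure the common practice. The window may therefore exist in controls. It would still start at a different stage of the illness.
4. **The gaps are trivial.** This is correct. With means rounded to whole numbers only exactly 80 is unassigned, and otherwise about 2 of 160 patients at most.

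**Conclusion.** The point holds as an inconsistency in one of six listed secondary outcomes. Two findings rest on the text alone: the three windows conflict, and the band above 180 contains the band above 240. The lack of comparability follows from the dosing time in the intervention group and the rule of no basal insulin before closure in controls. Its size is unknown. Because early observation can take in the initial high values, it could make the intervention group look worse.

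The size of the overlap, 0.4% to 34% of patients, rests wholly on the assumed normal distribution. It is not certain that the shares would exceed 100%. At the low end of the assumption they sum to 99%.

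Whole-stay averages may also give extra weight to the hourly readings taken during IVII (III.A), so infusion length could move the mean. The documents do not allow this to be sized, and the conclusion does not need it.

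The primary outcome and the sample size are unaffected.

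**What to change.** 1. **Choose one measure and one window.** Make the hyperglycemia outcome the incidence of any glucose above 180 mg/dL, in a window whose start is defined the same way in both groups. Use it in III.A, III.B, III.D and the data sheet, and name its test in Section V.
2. **Candidate window: 24 hours after IVII discontinuation.** It is already a data field, so it needs no new data, only the 180 mg/dL threshold written beside it. It has a drawback that the plan should state: if early glargine shortens the infusion, treatment itself affects when the window starts. It also changes the listed outcome, so it needs a protocol amendment.
3. **If the mean/median categories are kept, call them descriptive.** Either make them exclusive and exhaustive (<80, 80 to 100, >100 to 140, >140 to 180, >180 to 240, >240), or say that above 180 and above 240 are cumulative thresholds compared separately. Fix the choice of mean or median in advance.
4. **Add the readings that the categories need.** The listed variables hold initial glucose and event fields, but no serial, mean or median glucose. Keeping the categories means adding serial readings to the data sheet for both groups.

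Items 1 and 2 cost wording only. Item 4 costs extra data extraction and is avoided if the categories are dropped.
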